6.4.8.2. Laboratory Tests

Laboratory values will be summarized by treatment group, including the observed value, changes and percent changes from baseline at each time point.

A shift analysis using the normal range (except for eGFR and HbA1c) will be done which counts the number of subjects with a low, normal or high value at baseline and a low, normal or high value post baseline.

The following ranges will be used for eGFR and HbA1c

- For eGFR, the categories will be Severe = $<30 \text{ mL/min}/1.73\text{m}^2$; Moderate = $\ge 30 \text{ to } <60 \text{ mL/min}/1.73\text{m}^2$; Mild = $\ge 60 \text{ to } <90 \text{ mL/min}/1.73\text{m}^2$; and Normal = $\ge 90 \text{ mL/min}/1.73\text{m}^2$.
- For HbA1c, the categories will be $\leq 5.6\%$, $\geq 5.7\%$ to $\leq 6.4\%$, and $\geq 6.5\%$.

The baseline and worst post-baseline value will be utilized for the shift tables. Note that the shift table dealing with the fasting glucose parameter will require the lab sample to be taken while fasting. Samples taken while the subject was not fasting will not be analyzed.

The number and percentage of subjects with potentially clinically significant (PCS) laboratory values and clinically significant (CS) laboratory values (refer to Appendix 4 for the criteria) will be summarized by treatment group. Hemoglobin A1c criteria is explicitly stated in Appendix 4. All other PCS and CS criteria are met when both of the following occur:

- Post-baseline values meet the thresholds listed in Appendix 4
- Baseline values or any prior post-baseline values do not meet the thresholds listed in Appendix 4

PCS chemistry laboratory values will also be classified as follows:

- Abnormal baseline:
 - Non HbA1c: >1 and \leq 3x ULN at baseline and >1 and \leq 3x ULN at final visit
 - o HbA1c: ≥6.5% at baseline and ≥6.5% and ≥0.5% change from baseline at final visit

• Elevated further:

○ Non HbA1c: >1 and \leq 3x ULN at baseline or post baseline and becoming > 3x ULN post baseline

• Final visit:

- Non HbA1c: >1 and \leq 3x ULN at final visit only but not at baseline or previous visits
- o HbA1c: \geq 6.5% and \geq 0.5% change from baseline at final visit only but not at baseline or previous visits

• Persistently elevated:

- Non HbA1c: >1 and \leq 3x ULN at a post baseline visit and remains >1 and \leq 3x ULN until final visit
- HbA1c: \geq 6.5% and \geq 0.5% change from baseline at a post baseline visit and remains \geq 6.5% and \geq 0.5% change from baseline until final visit

• Resolved:

- o Non HbA1c: >1 and $\le 3x$ ULN at baseline or post baseline, resolved to < ULN at any post baseline visit, and remaining < ULN at final visit
- HbA1c: \geq 6.5% at baseline or \geq 6.5% and \geq 0.5% change from baseline for post-baseline, resolved to <6.5% and <0.5% change from baseline at any post baseline visit, and remaining <6.5% and <0.5% change from baseline at final visit

Separate listings of all subjects with PCS and CS laboratory values will be presented. Subjects will appear once per lab parameter but may appear under multiple lab parameters. The worst post-baseline value will be utilized in the analyses.

The number and percentage of subjects satisfying Hy's Law will also be tabulated by treatment group based on the following lab findings:

- Any elevated post-baseline aminotransferases defined as:
 - $ALT > 3 \times ULN \text{ or }$
 - AST $> 3 \times ULN$
- Elevated post-baseline serum total bilirubin (TBL) > 2 x ULN and serum alkaline phosphatase (ALP) levels < 2 x ULN

Subjects must meet all of the criteria listed above at the same time point and have normal lab parameters (ALT, AST, TBL) at baseline to be considered a Hy's Law case.

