- 2. The remaining missing values with a monotone missing data pattern will be imputed in this step. Control-based PMM imputation will be performed. With this imputation model, the missing efficacy measurements in the inclisiran group will not be constructed from the observed data in the inclisiran group but rather from the observed data in the placebo group. We will also use this model to impute missing efficacy measurements in the placebo group. The MNAR statement in SAS PROC MI will be used to impute missing values under the aforementioned assumptions. This will be performed for the 100 datasets. After this step, the 100 datasets will be fully imputed.
- 3. A total of 100 fully imputed datasets will be created (M=100). Since multiple imputation is a stochastic method, slight differences in output can be expected for different initial states of the random number generator. The seed numbers will be identified in the SAS programs to allow for reproducibility.

- 4. After the missing data imputation is completed using the above steps, absolute change/percentage change values will be calculated in each of the imputed datasets at each visit.
- 5. These 100 datasets will be analyzed using the MMRM described in Appendix 1 for the coprimary efficacy endpoints and key secondary efficacy endpoints.
- 6. Treatment effects (difference in LS means between treatments) from these 100 analyses will then be combined using Rubin's Method via SAS PROC MIANALYZE procedure for each endpoint.

APPENDIX 4. CRITERIA FOR POTENTIALLY CLINICALLY SIGNIFICANT AND CLINICALLY SIGNIFICANT ABNORMAL LABORATORY TESTS

Hemoglobin A1C criteria is explicitly stated in the table below.

All other criteria are met when both of the following occur:

- Post-baseline values meet the thresholds below
- Baseline values or any previous post-baseline values do not meet the thresholds below

Parameter	Unit	Lower Boundary	Upper Boundary
Hematology			
Hematocrit	%	≤0.8 × LLN	N/A
Hemoglobin	g/dL	≤10 g/dL	N/A
Platelet Count	10^9/ L	≤75*	≥700*
White Blood Cell Count	10^9/L	≤2.8	≥16
Serum Chemistry			1
Alanine Aminotransferase (ALT/SGPT)	U/L	N/A	>1 and $\leq 3 \times ULN$
Alanine Aminotransferase (ALT/SGPT)	U/L	N/A	>3 and $\leq 5 \times ULN*$
Alanine Aminotransferase (ALT/SGPT)	U/L	N/A	$>$ 5 and \leq 10 × ULN*
Alanine Aminotransferase (ALT/SGPT)	U/L	N/A	>10 and <20 × ULN*
Alanine Aminotransferase (ALT/SGPT)	U/L	N/A	>20 × ULN*
Alkaline Phosphatase	U/L	N/A	>2 × ULN*

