Aspartate Aminotransferase (AST/SGOT)	U/L	N/A	>1 and ≤3 × ULN
Aspartate Aminotransferase (AST/SGOT)	U/L	N/A	>3 and ≤5 × ULN*
Aspartate Aminotransferase (AST/SGOT)	U/L	N/A	>5 and ≤10 × ULN*
Aspartate Aminotransferase (AST/SGOT)	U/L	N/A	>10 and <20 × ULN*
Aspartate Aminotransferase (AST/SGOT)	U/L	N/A	>20 × ULN*
Creatine Kinase (CK)	U/L	N/A	>1 and ≤3 × ULN
Creatine Kinase (CK)	U/L	N/A	>3 and ≤5 × ULN
Creatine Kinase (CK)	U/L	N/A	>5 × and ≤10 x ULN*
Creatine Kinase (CK)	U/L	N/A	>10 and $\leq 20 \times ULN^*$
Creatine Kinase (CK)	U/L	N/A	>20 × ULN*
Hemoglobin A1C	%	N/A	≥6.5% and ≥0.5% change from baseline
Serum Creatinine	mg/dL	N/A	≥50% increase from Baseline or >2 mg/dL*
Total Bilirubin	mg/dL	N/A	>2 × ULN*

LLN: \underline{L} ower \underline{l} imit of the standard reference (\underline{n} ormal) range; ULN: \underline{U} pper \underline{l} imit of the standard reference (\underline{n} ormal) range; N/A is Not Applicable.

^{*}Clinically significant laboratory boundaries.

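### The PCS/CS laboratory rule does not say whether the baseline check is per band or per parameter; one reading counts improvements (mainly CK), the other omits worsening from an abnormal baseline

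*SAP*

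**What the plan says.** SAP 6.4.8.2 sets two conditions for every parameter except HbA1c. The first is "Post-baseline values meet the thresholds listed in Appendix 4". The second is that baseline values, or any "prior post-baseline values do not meet the thresholds listed in Appendix 4". Appendix 4 repeats the second condition with the words "previous post-baseline values do not meet the thresholds below".

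Most Appendix 4 parameters have a single cut-off in each direction. ALT, AST and CK instead have five rows each. For CK the rows are >1 to 3, >3 to 5, >5 to 10, >10 to 20 and >20 x ULN, and the top three are marked as clinically significant. Every row but the last has an upper limit; the third, for example, reads ">5 × and ≤10 x ULN".

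Two sentences on the listings also bear on the point: "Subjects will appear once per lab parameter but may appear under multiple lab parameters" and "The worst post-baseline value will be utilized in the analyses".

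Protocol 10.4.4.2 had limited these incidence rates to subjects with no PCS/CS value at baseline. SAP section 8 records that the identification of such values was changed, without saying how or why.

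**The concern.** A band with an upper limit is not met by a value above it. If the second condition is checked row by row, a high baseline does not meet a lower row, and a later fall into that row satisfies both conditions. An improving subject then enters the count of subjects with PCS or CS values.

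If the condition is checked across all rows of a parameter, that problem largely goes away, but a subject already in the lowest band at baseline cannot be counted on rising straight from it into a CS band.

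What is at stake is whether the by-arm PCS/CS counts and subject listings can be read as showing deterioration on treatment. CK is the parameter where this matters. Subjects on statins are to be at a maximally tolerated dose (Protocol 4.2), and CK is one of the laboratory values the protocol monitors for individual safety (Protocol 4.5.1).

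**Working it through.** The plan states no figure on this point, so the check applies the written rule to test values.

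**Inputs.** The two conditions come from SAP 6.4.8.2, the five CK rows from Appendix 4, and the use of the worst post-baseline value from 6.4.8.2. Let b be baseline and w the worst post-baseline value, both in multiples of ULN.

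- Per band: counted in a row if w lies in that row and b does not.
- Per parameter: counted in a row if w lies in that row and b lies in no row (b ≤ 1).
- Proposed: counted in a row if w lies in that row and b is at or below the row's lower bound.

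**Single cases.**

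| b → w | Per band | Per parameter | Proposed |
|---|---|---|---|
| 6 → 2 | counted, >1 to 3 | not counted | not counted |
| 12 → 6 | counted, >5 to 10 (CS) | not counted | not counted |
| 2 → 12 | counted, >10 to 20 (CS) | not counted | counted, >10 to 20 (CS) |
| 0.8 → 6 | counted, >5 to 10 (CS) | counted, >5 to 10 (CS) | counted, >5 to 10 (CS) |

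**All single steps over six levels** (0.8, 2, 4, 6, 15 and 25x: one below every row, and one in each row).

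- Falls from baseline: 6 × 5 / 2 = 15. Five end at 0.8x, below every row. The other 15 − 5 = 10 land in a lower row.
- Rises from an abnormal baseline: 5 × 4 / 2 = 10, each into a higher row.

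| Reading | Falls counted | Rises from abnormal baseline counted |
|---|---|---|
| Per band | 10 of 15 | 10 of 10 |
| Per parameter | 0 of 15 | 0 of 10 |
| Proposed | 0 of 15 | 10 of 10 |

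These fractions enumerate possible transitions. They do not estimate how often each occurs.

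**Sequences, read per band with the worst-value sentence applied.**

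- Baseline 6, then 2 and 2: counted in >1 to 3.
- Baseline 0.8, then 6 and 2: counted only in >5 to 10; the later 2x is ignored.
- Baseline 6, then 6 and 2: not counted.

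If the worst-value sentence governs only the listings, next to which it stands, the 2x value is counted in all three.

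**The words joining baseline and prior values.** Take baseline 6, then 0.8 and 2, read per parameter. If both baseline and all prior values must be clear, the 2x is not counted. If either suffices, it is counted, because the 0.8x meets no threshold. So the per-parameter reading also needs this wording settled.

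**Which reading is more natural.** SAP 6.4.8.2 goes on to classify PCS chemistry values by band. One class is the >1 to 3x band "at final visit only but not at baseline or previous visits". Another is a value in that band "ULN at baseline or post baseline and becoming > 3x ULN post baseline". There is no class for moving down into the band. Per band is also the only one of the two readings under which the upper rows can be reached directly from an abnormal baseline.

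**The case against.** The strongest reply is that per-band testing is an inference. The SAP refers only to the thresholds, and Protocol 10.4.4.2 is worded per subject, so a baseline in any row could be meant to block a flag. That stands as a limit on the claim: the SAP does not state that bands are tested one at a time. It does not rescue the rule, because the alternative counts none of the ten direct rises from an abnormal baseline.

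Four further points narrow the scope, and all stand.

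- The worst-value sentence refers to the analyses. If it covers the tables, a fall between two post-baseline values is not counted, so the issue is confined to subjects whose baseline is above their worst later value.
- Protocol 4.3, criterion 7 excludes confirmed unexplained ALT or AST above 3x ULN at screening. There is no CK limit. That leaves mainly CK above 3x ULN at baseline, with all later values in lower bands and the worst still above 1x. Seven post-baseline chemistry visits are scheduled, so this pattern may be uncommon.
- The same section plans observed values, changes at each visit and a shift table from baseline to worst value. A subject going from 6x to 2x appears there as high to high, so the earlier elevation stays visible.
- The tables are descriptive, and one rule applies to both randomised, blinded arms.

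A reader might infer that improvements mask real deterioration. On the per-band reading they do not: all ten rises are counted, and the class for values going above 3x reports worsening separately. A reader might also infer a bias between arms; nothing in the documents shows a direction.

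**Conclusion.** The rule needs correction. On the more natural reading, a subject whose baseline lies in a higher band and whose worst later value lies in a lower one is counted as meeting the criterion despite improving. On the other reading, a direct rise from an already abnormal baseline is left out. No other text in the SAP or its addendum resolves this.

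The consequence is limited to descriptive PCS/CS counts and listings, realistically for CK. Efficacy analyses are untouched. The number of subjects affected cannot be estimated, because the documents give no distribution of baseline CK. The conclusion assumes that the worst-value sentence applies to the tables; if it applies only to listings, falls between post-baseline visits are also counted and the issue is wider.

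**What to change.** In SAP 6.4.8.2 and Appendix 4, keep the existing bands for ALT, AST and CK. Count a subject in the band of the worst post-baseline value only if that band is higher than the baseline band, that is, if baseline is at or below the band's lower bound. Replace the reference to any prior post-baseline value with an explicit comparison to baseline, and say that the worst-value rule covers tables as well as listings.

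Cumulative cut-offs (>1, >3, >5, >10, >20x ULN) would also remove the counted falls, but they are not the same table. A subject going from 0.8x to 6x has one entry with bands and three with cut-offs (>1, >3 and >5), which blurs the PCS/CS split. Keeping the bands is the smaller change.

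The cost is one sentence, a small programming change and, compared with the per-band reading, slightly lower counts in some bands. The SAP addendum was written after unblinding, so a correction made now should be labelled as such. It could be shown beside the planned table, as the addendum does for its second liver-safety summary.

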4.5. Stopping Criteria

4.5.1. Individual Subject Dosing Stopping Criteria

During the double-blind, active treatment phase subjects will have clinic visits at regular intervals. Dosing with blinded study medication (inclisiran and/or matching placebo) should be temporarily discontinued or stopped in subjects with:

1. Intolerable adverse events, or if the Investigator believes that continuing dosing will be detrimental to the subject's mental or physical health. This includes severe or serious reactions at the injection site and any anaphylactic type reactions.
2. Unexplained increases in transaminases (ALT or AST) or total bilirubin as follows:
 - a. ALT or AST >8xULN
 - b. ALT or AST >5xULN for more than 2 weeks
 - c. ALT or AST >3xULN and (total bilirubin >2xULN or INR >1.5)
 - d. ALT or AST >3xULN with the appearance of fatigue, nausea, vomiting, right upper quadrant pain or tenderness, fever, rash, and/or eosinophilia (>5%)

The investigator should evaluate to see if other causes for the laboratory abnormalities are immediately apparent, such as obstructive gall bladder or bile duct disease, viral or alcoholic hepatitis, malignancy involving the liver, congestive hepatopathy, other hepatotoxins or heritable disorders.

3. Unexplained creatine kinase (CK) values $>5 \times$ ULN confirmed by repeat test when the CK elevation is associated with muscle pain, muscle tenderness and/or muscle weakness, or new onset renal dysfunction.

In the case that study medication is permanently discontinued the subject will be asked to complete the remainder of the scheduled visits without receiving blinded study medication (inclisiran or placebo).

All trial subjects should be followed until all abnormalities return to normal or to the baseline state.

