8.6.2. Sponsor Discontinuation Stopping Criteria

The Sponsor will review data on an ongoing basis and may, on discussion with the IDMC, terminate the study for any clinically significant drug related safety signal (eg. serious hypersensitivity reactions or drug induced liver injury, etc).

Premature termination of a study may also occur because of a regulatory authority decision, change in opinion of the IRB/EC, drug safety problems, or at the discretion of MDCO. In addition, MDCO retains the right to discontinue development of inclisiran at any time.

If a study is prematurely terminated or discontinued, MDCO will promptly notify the investigator. After notification, the investigator must contact all participating subjects and the hospital pharmacy (if applicable) within 30 days of the notification. Final study visits should occur within 30 days of subject contact. As directed by MDCO, all study materials must be collected and all eCRFs completed to the greatest extent possible.

The Sponsor will inform the health authorities and the IRBs/EC that the study has been stopped and the reasons for doing so, within the locally applicable timelines.

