3.8.8.3. Chemistry

Blood draws for chemistry will be performed per the Schedule of Assessments (Table 1). Analysis will vary based on visit day as follows:

• Full serum chemistry - Baseline (Day 1) and EOS (Day 540)

Aspartate aminotransferase (AST), alanine aminotransferase (ALT), alkaline phosphatase (ALP), gamma glutamyl transferase (GGT), total bilirubin (TBIL), direct and indirect bilirubin, creatine phosphokinase (CPK), lactate, bicarbonate, uric acid, creatinine, blood urea nitrogen (BUN), estimated glomerular filtration rate (eGFR), sodium, potassium,

calcium, inorganic phosphate, chloride, albumin, total protein, glucose (fasting), glycated hemoglobin A1C (HbA1c), and tryptase (as required).

• Limited serum chemistry - Screening, Days 90, 150, 270, 330, 450 and 510 ONLY: AST, ALT, ALP, GGT, TBIL, CPK, creatinine, eGFR, fasting glucose, HbA1c (not at Day 150, 330, and 510) and tryptase (as required).

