2.3. Laboratory Tests

The number and percentage of subjects satisfying Hy's Law will also be tabulated by treatment group based on the following lab findings:

- Any elevated post-baseline aminotransferases defined as:
 - $ALT > 3 \times ULN \text{ or }$
 - AST $> 3 \times ULN$
- Elevated post-baseline serum total bilirubin (TBL) > 2 x ULN and serum alkaline phosphatase (ALP) levels < 2 x ULN

Subjects must meet all of the criteria listed above at the same time point and have normal lab parameters (ALT, AST, TBL) at baseline to be considered a Hy's Law case. Per FDA feedback, a second summary will be presented that includes all subjects who meet all of the criteria listed above at the same time point without regard to the baseline lab parameter (ALT, AST, TBL) results.

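### Both Hy's Law tables require every limit to be met at one time point, so a subject whose bilirubin passes 2 x ULN only after ALT/AST has fallen back to 3 x ULN or below is counted in neither

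*SAP*

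**What the plan says.** SAP 6.4.8.2 (Laboratory Tests) tabulates Hy's Law cases by arm from two laboratory findings. The first, introduced as "Any elevated post-baseline aminotransferases defined as", is ALT or AST above 3 x ULN. The second is "Elevated post-baseline serum total bilirubin (TBL) > 2 x ULN" together with ALP below 2 x ULN. The counting rule follows: "Subjects must meet all of the criteria listed above at the same time point and have normal lab parameters (ALT, AST, TBL) at baseline".

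SAP Addendum 2.3 keeps that table and, on agency feedback, adds a second one that "includes all subjects who meet all of the criteria listed above at the same time point without regard to the baseline lab parameter". Only the baseline condition is removed.

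Neither place defines time point, gives a look-forward window, or plans a summary of peak ALT/AST against peak bilirubin. SAP 6.3.3 (Table 2) assigns draws to visit windows and, where several fall in one window, uses only the non-missing one nearest the nominal day.

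SAP 3.8.8.3 schedules liver chemistry as "Limited serum chemistry - Screening, Days 90, 150, 270, 330, 450 and 510", with the full panel on Day 1 and Day 540.

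**The concern.** The Hy's Law count is the only planned summary that combines aminotransferases with bilirubin. Its rule looks at one time point at a time. If ALT/AST passes its limit at one draw, and bilirubin passes its own limit only at a later draw when ALT/AST is back to 3 x ULN or below, no single time point meets every criterion. The addendum's relaxation does not help such a subject, because it concerns baseline values and not timing.

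The stake is a liver-safety count in a trial of a drug taken up by hepatocytes (Protocol 1.2). Protocol 8.6.2 gives "serious hypersensitivity reactions or drug induced liver injury" as examples of signals on which the sponsor may terminate the study. Any such count is likely to be zero or very small, so one subject can decide whether the table shows none or one.

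**Working it through.** The plan attaches no rate, power or sample size to this definition, so there is no stated figure to reproduce. The check applies the rule to example sequences, then looks at the visit schedule, the windowing rule and the size of one case.

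**1. The rule applied to four illustrative sequences.** Values are multiples of ULN, baseline is normal, and the ALT column stands for the higher of ALT and AST. Both draws are taken as separate time points. A case needs one draw with ALT > 3, TBL > 2 and ALP < 2.

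| Sequence | Draw 1 (ALT, TBL, ALP) | Draw 2 (ALT, TBL, ALP) | SAP table | Addendum table |
|---|---|---|---|---|
| a. All limits met at one draw | 4, 2.5, 1.2 | 1, 1, 1 | case | case |
| b. TBL later, ALT fallen back | 6, 1.2, 1.2 | 2.5, 2.5, 1.2 | no case | no case |
| c. TBL later, ALT still above 3 | 6, 1.2, 1.2 | 4, 2.5, 1.2 | case | case |
| d. TBL later, ALP now 2 or more | 6, 1.2, 1.2 | 4, 2.5, 2.1 | no case | no case |

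With an abnormal baseline the SAP table counts none of the four, and the addendum table gives the results shown. Sequences b and d are lost in both tables; sequence c is not.

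**2. Spacing of scheduled draws.** From Days 1, 90, 150, 270, 330, 450, 510 and 540 (SAP 3.8.8.3), the gaps are 90 - 1 = 89, 150 - 90 = 60, 270 - 150 = 120, 330 - 270 = 60, 450 - 330 = 120, 510 - 450 = 60 and 540 - 510 = 30 days. After Day 90, consecutive scheduled draws are thus 30 to 120 days apart, so the two limits can fall at different draws. How often they would do so cannot be derived from the documents.

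**3. The undefined time point.** Suppose it means a Table 2 window. Take Day 90 with ALT 6 x ULN and normal bilirubin, then an unscheduled Day 100 repeat with ALT 4 x ULN, bilirubin 2.5 x ULN and ALP below 2 x ULN. Both lie in the Day 61 to Day 120 window. The nearest-day rule keeps Day 90 and drops Day 100, although Day 100 alone meets every criterion. Section 6.4.8.2 does call for worst post-baseline values in its shift tables and its PCS/CS listings. It does not say whether the Hy's Law count likewise runs over all draws. Repeat draws are foreseeable, since Protocol 4.5.1 and 5.3.1 require abnormal findings to be followed.

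**4. What one subject changes.** Assume an even split of the 482 enrolled with all dosed: 482/2 = 241 per arm. The two-sided exact 95% upper limit p solves:
- 0 of 241: (1 - p)^241 = 0.025, so p = 1 - 0.025^(1/241) = 1.5%.
- 1 of 241: (1 - p)^241 + 241p(1 - p)^240 = 0.025, so p = 2.3%.

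The rule of three (3/241 = 1.2%) should not be set beside 2.3%: it approximates a one-sided 95% limit and would exaggerate the contrast.

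**The case against.** The strongest reply is that detection is already covered and only a cross-tabulation is missing. ALT and AST bands above 3 x ULN and bilirubin above 2 x ULN are each clinically significant in SAP Appendix 4. They are counted by arm and listed, and a subject can appear under several parameters. SAP 6.3.3 puts all data into subject listings, Appendix 5 searches hepatic adverse-event terms, and the IDMC reviews safety every 3 months. This stands in part: a subject like sequence b could be found by cross-reading. But the PCS/CS listings show each subject once per parameter at the worst value, so they do not promise the sequence in time, and no combined count would include that subject.

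The agency has also commented on this table, and the addendum postdates database lock and unblinding, so any further definition is post hoc. That is a reason to label a new table supplementary. Feedback about the baseline condition does not show that concurrency alone is enough.

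Several stronger inferences are tempting and should be resisted:
- That any later bilirubin rise is missed. Sequence c shows otherwise: if the later draw is used, and ALT/AST is still above 3 x ULN with ALP below 2 x ULN, the subject is counted.
- That such separation is usual. The documents give no rate.
- That the rule can err only by missing cases. Neither table excludes other causes, and the addendum table ignores baseline values, so either can also count subjects who are not true cases.
- That the protocol contradicts the SAP. Stopping criterion 2c, "ALT or AST >3xULN and (total bilirubin >2xULN or INR >1.5" in part, is an individual dosing rule for unexplained rises and is silent on timing. Silence is neither a conflict nor an endorsement of non-concurrent values.

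**Conclusion.** The gap is real and narrow. Both tables omit a subject whose bilirubin exceeds 2 x ULN only at a draw where ALT/AST is 3 x ULN or lower, or where ALP has reached 2 x ULN. No other planned summary counts the combination. Under the window reading of time point, a repeat draw that qualifies on its own could be lost as well.

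The number of subjects affected is unknown. If one subject moved a count from 0 to 1, the upper limit would move from 1.5% to 2.3%, on the assumption of 241 dosed subjects per arm. The omission itself follows from the rule as written and needs no assumption about how liver injury usually evolves. No efficacy result depends on it. It is a worthwhile, inexpensive improvement to safety reporting, not a flaw that invalidates the existing tables.

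**What to change.** Keep both tables. For them, define time point as a single blood draw, scheduled or unscheduled, and exempt these counts from the nearest-day rule in SAP Table 2.

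Add one table, labelled supplementary, of subjects with:
- ALT or AST above 3 x ULN at any post-baseline draw;
- ALP below 2 x ULN at that draw;
- total bilirubin above 2 x ULN at that draw or a later one.

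Use all scheduled and unscheduled values. All four sequences above would then appear. List dated serial ALT, AST, bilirubin and ALP values for each subject found.

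If a look-forward window is imposed, state its length as an analysis choice. At nominal days a 30-day window reaches a second scheduled draw only from Day 510 to Day 540; elsewhere it would depend on unscheduled repeats.

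The cost is one table and one listing from data already collected. The downside is lower specificity: some subjects with unrelated bilirubin rises will appear and need individual review. This changes the analysis only and implies nothing about the dosing stopping criteria.
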